### 3.3. EXPLORATORY OBJECTIVES

The exploratory objectives of the study are as follows:

- To assess the effects of ATX-GD-59 on TSHR induced Peripheral Blood Mononuclear Cell (PBMC) T-cell activity.
- To assess the effects of ATX-GD-59 on the T-cell cytokine signature.
- To assess the effects of ATX-GD-59 IL-10 pathway and associated genes expression (Messenger Ribonucleic Acid [mRNA]).

## 4. STUDY DESIGN

### 4.1. GENERAL DESCRIPTION

This is a phase I, first in human, open-label within subject dose-escalating study to evaluate the safety and efficacy of ATX-GD-59 in approximately 12 evaluable subjects with Graves' disease who are HLA-DRB1\*15, HLA-DRB1\*03 and/or HLA-DRB1\*04 positive and not currently treated with anti-thyroid therapy.

There will be an upward titration over five dose levels (injection(s) of 25, 50, 100, 400 and 800 µg) of ATX-GD-59, followed by a further five injections of the highest dose (expected to be 800 µg total peptide). All doses are based on the total peptide.

No control group will be utilized in this study and all subjects will receive the same dose-escalation schedule of ATX-GD-59.

All doses will be administered by intradermal injection to the anterior abdominal wall or thigh at intervals of 14 +/- 3 days.

---

Document: ATX\_GD\_59 Final 1.0 SAP 28FEB2018.docx  
Author: [name]

Version Number: Final 1.0  
Version Date: 28FEB2018

Template No: CS\_TP\_BS016 Revision 4  
Effective Date: 01Apr2016

Reference: CS\_WI\_BS005

Copyright © 2009, 2010, 2012, 2016 Quintiles Transnational Corp. All rights reserved.  
The contents of this document are confidential and proprietary to Quintiles Transnational Corp. Unauthorized use, disclosure or reproduction is strictly prohibited.

## 4.2. SCHEDULE OF EVENTS

Activity	Screen n	Titration Period					Full dose Treatment Period					Follow-up		*ET /USV	
		W -4	SD1	W 2	W 4	W 6	W 8	W 10	W 12	W 14	W 16	W 18	W 22	W 30	
Investigational Medicinal Product dose (µg)	0	25	50	100	400	800	800	800	800	800	800	800	0	0	0
Informed Consent prior to Screening (week-4)	•														
Demographics	•														
Inclusion/Exclusion Criteria	•	•													
Medical History 	•														
Family History of Autoimmune Disease	•														
Graves' disease History	•														
Physical Examination 	•	•	•	•	•	•	•	•	•	•	•	•			•
Vital signs 	•	•	•	•	•	•	•	•	•	•	•	•	•	•	•
12 lead ECG 	•	•	•	•	•	•	•	•	•	•	•	•			
Issue new diary/diary review		•	•	•	•	•	•	•	•	•	•	•			•
Adverse Event Recording	•	•	•	•	•	•	•	•	•	•	•	•	•	•	•
Injection site reaction assessment		•	•	•	•	•	•	•	•	•	•	•			•
Concomitant Medications/Procedures	•	•	•	•	•	•	•	•	•	•	•	•	•	•	•
Haematology & Chemistry Tests 	•	•	•	•	•	•	•	•	•	•	•	•	•	•	•
Analysis and ratio of stimulatory vs inhibitory THSR antibodies	•	•	•	•	•	•	•	•	•	•	•	•	•	•	•
Urine/serum Pregnancy Test 	•	•		•		•		•		•		•	•	•	•
Urine Analysis	•	•	•	•	•	•	•	•	•	•	•	•	•	•	•
HLA Typing	•														
Anti-drug antibody test	•							•		•		•	•		•
Blood Sampling for specific T cell activity assay, additional Immunological Biomarkers  and IL-10 pathway and associated genes (mRNA).	•											•	•		•

Document: ATX\_GD\_59 Final 1.0 SAP 28FEB2018.docx  
 Author: [name]

Version Number: Final 1.0  
 Version Date: 28FEB2018

Template No: CS\_TP\_BS016 Revision 4  
 Effective Date: 01Apr2016

Reference: CS\_WI\_BS005

1. Significant medical history as determined by the investigator to be recorded (including a history of autoimmune diseases).
2. Include height at week -4 only.
3. Respiration rate, systolic blood pressure (SBP), diastolic blood pressure (DBP), heart rate, oral body temperature, recorded after the subject has been sitting quietly for at least 5 minutes.
4. Electrocardiogram (ECG) and Vital signs will be measured pre and post dose.
5. Blood samples to be drawn prior to dosing.
6. Serum pregnancy test at week -4 only. Urine dipstick test for all subsequent visits.

\* Early Termination (ET) is performed if the subject is withdrawn between Study Day 1 (SD1) and Week 22.  
Unscheduled visit performed at any time during the study. Number of blood tests required to be agreed with the study medical monitor.

## 4.3. CHANGES TO ANALYSIS FROM PROTOCOL

### 4.3.1. POPULATIONS

The Per-protocol (PP) population requirements stated in the protocol (see section 20.4.2) included subjects required to receive the full treatment regimen (i.e., all doses received and at least 80% of protocol-specified total study drug volume injected for the entire treatment period). Compliance with respect to study drug volume ( $\mu$ L) injected will be replaced by compliance with respect to total study drug dose ( $\mu$ g) injected. Since the eCRF records changes from planned dose injected, not changes from planned dose volume injected and the direct calculation between study drug dose and volume, this change was implemented for consistency for reporting of study drug dosing data. Further the PP population will only be summarised separately, if it represents at least 50% of the total Intention-to-treat (ITT) population and is different from the ITT population by at least one subject.

The definition of the anti-thyroid drug population in the protocol (see section 20.4.3) is defined as the PP population plus those who had received anti-thyroid drugs during the ATX-GD-59 dosing and follow-up period to Week 22. Following a discussion with Apitope, the definition for the anti-thyroid drug population for analysis was updated to any ITT subject taking anti-thyroid drugs at any time post first dose of ATX-GD-59 up to and including the Week 22 visit. Further, this population will only be summarised separately, if it represents at least 50% of the total ITT population and is different from the ITT population by at least one subject.

### 4.3.2. BASELINE DEFINITION

The baseline for Vital Signs in the protocol (section 20.13) is defined as Screening (Week -4). Following a discussion with Apitope, the following baseline definition will be used instead “Baseline is defined as the last available (scheduled or unscheduled) assessment prior to the first administration of study drug”.

---

Document: ATX\_GD\_59 Final 1.0 SAP 28FEB2018.docx  
Author: [name]

Version Number: Final 1.0  
Version Date: 28FEB2018

Template No: CS\_TP\_BS016 Revision 4  
Effective Date: 01Apr2016

Reference: CS\_WI\_BS005

#### **4.3.3. COMPLIANCE**

Actual study drug volume ( $\mu$ L) injected, total study drug volume administered and percentage compliance with respect to volume injected will not be summarised or listed. This change from the protocol section 20.6 will be implemented since the eCRF records changes from planned dose injected, not changes from planned dose volume injected, and the latter can be directly derived from study drug dose administered, hence compliance can be determined based on study drug dose ( $\mu$ g) injected only.

#### **4.3.4. EFFICACY ASSESSMENTS**

The protocol (section 20.7) noted that the definition of responder to be used in the analysis would be defined in the SAP. A responder endpoint will however not be defined or used due to the small sample size and loss of information about magnitude of response due to the required dichotomisation needed and no published information on what is considered a clinically relevant cut-off between response and no response. Percentage change from baseline in addition to change from baseline at each time point for FT3, FT4 and TSH will be presented and summarised. Shifts to within and outside normal and abnormal range compared with baseline and incidence of markedly abnormal laboratory results will also be presented for the thyroid function tests.

#### **4.3.5. ADVERSE EVENTS**

Descriptive analysis of AEs will include frequency of events (AEs) in addition to incidence of subjects within each treatment period and dose level, to facilitate description of multiple reports of events of the same System Organ Class (SOC) or Preferred Term (PT).

The definition of post-treatment AEs stated in the protocol (section 20.9) was any AEs starting post treatment, commencing at Week 22. This was amended to AEs started or worsening after 28 days following last study drug treatment. This is to accommodate a variable Week 22 visit (window +/-3 days) and any ET visits where there is no Week 22 visit.

#### **4.3.6. CONCOMITANT MEDICATIONS**

Descriptive analysis of concomitant medications will include frequency of medications in addition to incidence of subjects within each treatment period, to facilitate description of multiple reports of medications of the same SOC or PT. The treatment period will also be sub-divided into the titration period and full treatment period.

---

Document: ATX\_GD\_59 Final 1.0 SAP 28FEB2018.docx  
Author: [name]

Version Number: Final 1.0  
Version Date: 28FEB2018

Template No: CS\_TP\_BS016 Revision 4  
Effective Date: 01Apr2016

Reference: CS\_WI\_BS005

Copyright © 2009, 2010, 2012, 2016 Quintiles Transnational Corp. All rights reserved.  
The contents of this document are confidential and proprietary to Quintiles Transnational Corp. Unauthorized use, disclosure or reproduction is strictly prohibited.

#### 4.3.7. PROCEDURES

Procedure period will also include 'prior' in order to identify in the listings and summarise any procedures occurring prior to first study drug administration. The treatment period will also be subdivided into the titration period and full treatment period for listings and summaries.

#### 4.3.8. SUMMARIES OF SAFETY AND EFFICACY ENDPOINTS

All study visits up to and including Week 30 will be presented in summaries of safety and efficacy endpoints which are summarised by scheduled visit. The protocol (sections 20.7 and 20.8) specifies that visits up to Week 22 will be summarised.

---

Document: ATX\_GD\_59 Final 1.0 SAP 28FEB2018.docx  
Author: [name]

Version Number: Final 1.0  
Version Date: 28FEB2018

Template No: CS\_TP\_BS016 Revision 4  
Effective Date: 01Apr2016

Reference: CS\_WI\_BS005

Copyright © 2009, 2010, 2012, 2016 Quintiles Transnational Corp. All rights reserved.  
The contents of this document are confidential and proprietary to Quintiles Transnational Corp. Unauthorized use, disclosure or reproduction is strictly prohibited.

## 5. PLANNED ANALYSES

The following analyses will be performed for this study:

- Interim safety analysis
- Final analysis

### 5.1. DATA MONITORING COMMITTEE

No analyses will be performed by IQVIA Biostatistics. IQVIA Data Management will produce the required listing output for the interim safety analysis review by the Data Review Committee (DMC) (see Data Monitoring Committee Plan, version 2.0, 10 February 2017).

### 5.2. FINAL ANALYSIS

All final, planned analyses identified in this SAP will be performed by IQVIA Biostatistics following Apitope authorisation of this SAP, relevant set of the Table, Listing and Figure (TLF) shells, the final population assignments and database lock.

See Appendix 4: Population Assignment and Data Review (DR) Plan for details pertaining the requirements for the DR meeting and outputs to be produced.

### 5.3. STUDY POPULATION

The Study population corresponds to all enrolled subjects, i.e. all subjects eligible for enrolment into the study. All data listings will be based on the Study population. Screen failures (including the initial screen of re-screened subjects) will be included in the disposition, demographics and eligibility listings of all subjects (i.e., all subjects providing written informed consent), and the number of screen failures will be summarised in the Study Disposition table.

---

Document: ATX\_GD\_59 Final 1.0 SAP 28FEB2018.docx  
Author: [name]

Version Number: Final 1.0  
Version Date: 28FEB2018

Template No: CS\_TP\_BS016 Revision 4  
Effective Date: 01Apr2016

Reference: CS\_WI\_BS005

Copyright © 2009, 2010, 2012, 2016 Quintiles Transnational Corp. All rights reserved.  
The contents of this document are confidential and proprietary to Quintiles Transnational Corp. Unauthorized use, disclosure or reproduction is strictly prohibited.

## 5.4. ANALYSIS POPULATIONS

### 5.4.1. INTENTION-TO-TREAT [ITT]/ SAFETY POPULATION

A primary ITT population will be defined for use in presenting baseline, efficacy and safety data. The ITT population corresponds to all subjects who received at least one administration of study drug at any time during the study, irrespective of compliance with eligibility and other protocol criteria.

The Safety population will be denoted as the 'ITT population' for the summarisation of safety endpoints.

### 5.4.2. PER-PROTOCOL [PP] POPULATION

A secondary PP population (i.e. the evaluable subjects) will be used to also consider all efficacy data, and is defined as all ITT subjects who complied with the protocol requirements. Subjects will need to have complied with the protocol (i.e. no major protocol deviations) up to and including the Week 22 visit, criteria to include (but not limited to):

- Met all inclusion and none of the exclusion criteria on study entry,
- Received the full treatment regimen (i.e. all doses received and at least 80% of protocol-specified total study drug dose (μg) injected for the entire treatment period, to be confirmed at the DR meeting),
- Not taken prohibited medications during the treatment period.
- Procedure done with consent.
- Not received anti-thyroid drugs prior to the Week 22 visit.

Efficacy parameters will be summarised for the PP population provided that it differs from the ITT population by at least one subject and is at least 50% of the ITT population.

Major protocol deviations determined programmatically, as well as the 'Protocol Deviations' log recorded in the IQVIA Clinical Trial Management System (CTMS) will be reviewed for determination of any further major deviations, to be included as reasons for exclusion from the PP population in the population assignment listing.

---

Document: ATX\_GD\_59 Final 1.0 SAP 28FEB2018.docx  
Author: [name]

Version Number: Final 1.0  
Version Date: 28FEB2018

Template No: CS\_TP\_BS016 Revision 4  
Effective Date: 01Apr2016

Reference: CS\_WI\_BS005

Copyright © 2009, 2010, 2012, 2016 Quintiles Transnational Corp. All rights reserved.  
The contents of this document are confidential and proprietary to Quintiles Transnational Corp. Unauthorized use, disclosure or reproduction is strictly prohibited.

#### 5.4.3. ANTI-THYROID DRUG POPULATION

A third analysis population, the anti-thyroid drug population, is defined as any ITT subject taking anti-thyroid drugs at any time post first dose of ATX-GD-59 to the Week 22 visit.

Efficacy parameters will be summarised for the anti-thyroid drug population provided that it differs from the ITT population by at least one subject and is at least 50% of the ITT population.

All data will be listed for subjects in the anti-thyroid drug population, however, only data up to the time point of dosing with anti-thyroid drugs will be included in summary tables of efficacy (TSHR antibodies and thyroid function tests for subjects in the anti-thyroid drug population). Additionally, visits post administration of anti-thyroid drugs in these subjects will be flagged in all by-visit listings of efficacy and safety data except diary card recordings of injection site reactions, and listings of exploratory efficacy parameter data (B set).

---

Document: ATX\_GD\_59 Final 1.0 SAP 28FEB2018.docx  
Author: [name]

Version Number: Final 1.0  
Version Date: 28FEB2018

Template No: CS\_TP\_BS016 Revision 4  
Effective Date: 01Apr2016

Reference: CS\_WI\_BS005

Copyright © 2009, 2010, 2012, 2016 Quintiles Transnational Corp. All rights reserved.  
The contents of this document are confidential and proprietary to Quintiles Transnational Corp. Unauthorized use, disclosure or reproduction is strictly prohibited.

## 6. GENERAL CONSIDERATIONS

### 6.1. REFERENCE START DATE AND STUDY DAY

Study Day will be calculated from the reference start date, and will be used to present start/ stop day of assessments and study events relative to the reference start date.

Reference start date is defined as the first administration date of study drug (Study Day 1).

- If the date of the assessment/event is on or after the reference start date then:

Study Day = (date of assessment/event – reference start date) + 1.

- If the date of the assessment/event is prior to the reference start date then:

Study Day = (date of assessment/event – reference start date).

In the situation where the assessment/event date is partial or missing, Study Day, and any corresponding durations will appear missing in the listings.

### 6.2. BASELINE

Unless otherwise specified, baseline is defined as the last available assessment (scheduled or unscheduled) prior to the first administration of study drug. In the case where the last non-missing measurement prior to first administration of study drug and the reference start date coincide, that measurement will be considered baseline.

Baseline and at each scheduled post-baseline visit as well as separately for multiple assessments within a visit, change from pre-dose to each post-dose assessment will also be evaluated.

### 6.3. POST-BASELINE

Unless otherwise specified, post-baseline is defined as any assessment (scheduled or unscheduled) obtained after the first study drug administration.

---

Document: ATX\_GD\_59 Final 1.0 SAP 28FEB2018.docx  
Author: [name]

Version Number: Final 1.0  
Version Date: 28FEB2018

Template No: CS\_TP\_BS016 Revision 4  
Effective Date: 01Apr2016

Reference: CS\_WI\_BS005

Copyright © 2009, 2010, 2012, 2016 Quintiles Transnational Corp. All rights reserved.  
The contents of this document are confidential and proprietary to Quintiles Transnational Corp. Unauthorized use, disclosure or reproduction is strictly prohibited.

## 6.4. RETESTS, UNSCHEDULED VISITS AND EARLY TERMINATION DATA

In general, for by-visit summaries, data recorded at the nominal visit will be presented. Unscheduled measurements will not be included in by-visit summaries. In the case of a retest (same visit number assigned), the earliest available measurement for that visit will be used for by-visit summaries.

The Early termination (ET) visits will be reviewed at the DR meeting, and it will be determined for each ET visit, whether it will be included in summary tabulations in place of the scheduled visit (where the ET visit has occurred in place of the scheduled visit and is within the relevant visit window) or presented separately (where the ET visit is not in a scheduled visit window). All ET visits will be listed as ET visits in the data listings.

Listings will include scheduled, unscheduled, retest and ET assessment data.

## 6.5. WINDOWING CONVENTIONS

No visit windowing will be performed for this study, except for ET visits as specifically described in this SAP (see section 6.4).

## 6.6. STATISTICAL TESTS

No formal statistical testing will be carried out for the analyses of the data from this study. All data presentations will be descriptive only.

The default summary statistics for quantitative variables will be as follows:

- Number of subjects in each category (n)
- Mean
- Standard deviation (SD)
- Minimum
- 25th Percentile (Q1) (Efficacy outcomes)
- Median
- 75th Percentile (Q3) (Efficacy outcomes)
- Maximum
- Geometric Mean (Efficacy outcomes with exception of percentage change from baseline)
- 95% Confidence Interval (CI) based on geometric mean (Efficacy outcomes with exception of percentage change from baseline)
- Correlation coefficient (r) (Exploratory efficacy outcomes)
- P-value (Exploratory efficacy outcomes)

---

Document: ATX\_GD\_59 Final 1.0 SAP 28FEB2018.docx  
Author: [name]

Version Number: Final 1.0  
Version Date: 28FEB2018

Template No: CS\_TP\_BS016 Revision 4  
Effective Date: 01Apr2016

Reference: CS\_WI\_BS005

Copyright © 2009, 2010, 2012, 2016 Quintiles Transnational Corp. All rights reserved.  
The contents of this document are confidential and proprietary to Quintiles Transnational Corp. Unauthorized use, disclosure or reproduction is strictly prohibited.

The default summary statistics for qualitative variables will be as follows:

- Number of subjects in each category (n).
- The percentages of subjects in each category (%) can be presented relative to either one of the following:
  - The total number of subjects in the relevant analysis population.
  - The total number of subjects in the relevant analysis population, with assessments available (observed cases).

If the original data has N decimal places, then the summary statistics should have the following decimal places:

- Minimum, maximum: N
- Mean, geometric mean, median, Q1, Q3 and 95% CI: N + 1
- SD: N + 2
- r: 3
- P-value: 4
- Fold change: 1

Frequencies and percentages (n and %):

- Percentage values should be reported inside parentheses, with one space between the count and the left parenthesis of the percentage.
- Percentages of subjects should be rounded to whole numbers. Percentages of events will be reported to one decimal place.

## 6.7. COMMON CALCULATIONS

### 6.7.1. CHANGE FROM BASELINE

For quantitative measurements, change from baseline will be calculated as:

- Test Value at Visit X (pre-dose or post-dose [if applicable]) – Baseline Value.
- For vital signs and 12-lead ECG findings, post-dose values at each post-baseline visit.

---

Document: ATX\_GD\_59 Final 1.0 SAP 28FEB2018.docx  
Author: [name]

Version Number: Final 1.0  
Version Date: 28FEB2018

Template No: CS\_TP\_BS016 Revision 4  
Effective Date: 01Apr2016

Reference: CS\_WI\_BS005

Copyright © 2009, 2010, 2012, 2016 Quintiles Transnational Corp. All rights reserved.  
The contents of this document are confidential and proprietary to Quintiles Transnational Corp. Unauthorized use, disclosure or reproduction is strictly prohibited.

### **6.7.2. PERCENTAGE CHANGE FROM BASELINE**

For FT3, FT4 and TSH, percentage (%) change from baseline will be calculated as:

- $(\text{Post-dose value} - \text{Baseline value}) / \text{Baseline value} * 100$

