Inclusion criteria

1. A diagnosis of Graves' disease as assessed by a physician from clinical and laboratory findings and not receiving anti-thyroid therapy.
2. Quantifiable levels of TSHR antibodies.
3. Raised levels of free T3 and/or free T4 (not exceeding 15 pmol/L and 35 pmol/L respectively) including undetectable levels of thyroid stimulating hormone.
4. HLA-DRB1*15, HLA DRB1*03 and or HLA DRB1*04 positive.
5. Age 18 – 65 years inclusive at the time of informed consent.
6. The subject must be willing and able to give written informed consent and must be willing to comply with protocol assessments/procedures.
7. Male subjects must be sterile (biologically or surgically) or commit to the use of a reliable method of birth control for the duration of the study until at least 90 days after the last dose of ATX-GD-59.
8. Female subjects of child bearing potential must:
 - neither be pregnant nor breast-feeding, nor attempting to conceive, and
 - use a highly effective method of contraception as defined below, throughout the entire duration of the study and for at least 90 days after the last dose of ATX-GD-59.

A serum pregnancy test will be performed at the screening visit in women of child bearing potential. Thereafter urine pregnancy tests will be performed. A positive result will exclude the woman from the study immediately.

A highly effective method of contraception is defined as those which result in a low failure rate when used consistently and correctly such as implants, injectable, combined oral contraceptives, some Intrauterine Devices (IUDs), unless post-menopausal or surgically sterilized. Barrier forms of contraception are considered appropriate when used in combination with one of the above methods.

Exclusion criteria

1. Subjects who are pregnant or breastfeeding and/or subjects in the post-partum period.
2. A known history of, or hypersensitivity reactions that in the opinion of the investigator would exclude the subjects' participation in the study.
3. Treatment with any Anti-Thyroid Drugs e.g. carbimazole within the previous 3 months prior to Study Day 1.
4. Previous treatment with radioiodine or (partial or complete) thyroidectomy.
5. Signs of moderate or severe orbitopathy including optic nerve compression requiring steroids and/or a clinical activity score >3.
6. Large and compressive goitres causing localised symptoms such as difficulty swallowing or breathing.

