#### 14.1.3.3. FT3, FT4 and TSH serum levels

TSH level results that are below the limit of quantitation (BLQ) will be treated as value for descriptive statistics but presented as ' $<$  value', in listings. The BLQ levels will be confirmed by Apitope or the IQVIA Central Laboratory prior to database lock.

The following summaries will be provided for the Thyroid function tests serum level data:

- Descriptive statistics (observed, change from baseline and percentage change from baseline) will be presented for each parameter at baseline and at each post-baseline visit for each analysis population as applicable.
- Shift from baseline to each scheduled protocol post-baseline visit for FT3, FT4 and TSH serum levels categorised according to normal reference range as low, normal and high, as well as a subcategory for markedly high. The high and markedly high categories are not mutually exclusive, thus the markedly high results will be included in the high category count. For the shift the percentage (%) of subjects in each category calculated relative to the total number of subjects in the relevant analysis population with assessments available at baseline and the relevant post-baseline visit per parameter.
- Incidence of markedly high results per time point of FT3 ( $>20$  pmol/L) and FT4 ( $>45$  pmol/L) for the ITT population.

Only data up to the time point of dosing with anti-thyroid drugs will be included in summary tables and figures of efficacy for subjects in the anti-thyroid drug population.

The following figures will be presented for the ITT population:

- Line graph of geometric means  $\pm$  95% CI limits (geometric) for FT3 and FT4.
- Line graph of change from baseline and percentage change from baseline means  $\pm$  SD for FT3 and FT4.
- Line graph of individual FT3 and FT4 results over time. Horizontal dotted lines will indicate the normal range lower and upper limits for each parameter.

---

Document: ATX\_GD\_59 Final 1.0 SAP 28FEB2018.docx  
Author: [name]

Version Number: Final 1.0  
Version Date: 28FEB2018

Template No: CS\_TP\_BS016 Revision 4  
Effective Date: 01Apr2016

Reference: CS\_WI\_BS005

- Scatter plots of each of change from baseline and percentage change from baseline versus baseline levels for FT3 and FT4 at Week 18, 22 and 30 will be presented with different colours/symbols on the same graph.

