## **15.2. LABORATORY EVALUATIONS**

Blood samples for haematology, and biochemistry and urine samples for urinalysis will be collected and eCRF entries made for the collection date/time and reason for non-collection if applicable. The

---

Document:	ATX_GD_59 Final 1.0 SAP 28FEB2018.docx	Version Number:	Final 1.0
Author:	[name]	Version Date:	28FEB2018

Template No: CS\_TP\_BS016 Revision 4  
Effective Date: 01Apr2016

Reference: CS\_WI\_BS005

Investigator is to review the laboratory report promptly, document this review, and record any clinically relevant changes occurring during the study on the Adverse Events eCRF.

Laboratory safety assessments will be assayed by Q2 Solutions Central Laboratory.

Results from the central laboratory will be included in the reporting of this study for Haematology, Biochemistry and Urinalysis. For a list of the clinical laboratory assessments to be included in the outputs together with their conversion factor to Système International (SI) units, refer to Appendix 3: Conversion Factors to Système International (SI) Units of this SAP.

Presentations will use SI units.

Quantitative laboratory measurements reported as “< X”, i.e. below the lower limit of quantification (BLQ), or “> X”, i.e. above the upper limit of quantification (ULOQ), will be converted to X for the purpose of quantitative summaries, but will be presented as recorded, i.e. as “< X” or “> X” in the by-subject listings.

The following summaries will be provided for laboratory data for the ITT population:

- Descriptive statistics (observed and change from baseline) will be presented for quantitative measurements of Haematology, Biochemistry and Urinalysis laboratory results at baseline and the scheduled protocol post-baseline visits (excluding FT3, FT4 and TSH that will be summarised separately under efficacy).
- Frequency count for markedly abnormal results will be presented for quantitative measurements of Haematology, Biochemistry and Urinalysis laboratory results by visit and dose level (excluding FT3, FT4 and TSH that will be summarised separately under efficacy).

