**Note:**

Only scheduled visits adherence applicable to the study is to be validated according to the relevant visit window below. Visits not in accordance with the table below are to be identified by means of a flag on the listing of study visits:

---

Document: ATX\_GD\_59 Final 1.0 SAP 28FEB2018.docx  
Author: [name]

Version Number: Final 1.0  
Version Date: 28FEB2018

Template No: CS\_TP\_BS016 Revision 4  
Effective Date: 01Apr2016

Reference: CS\_WI\_BS005

Copyright © 2009, 2010, 2012, 2016 Quintiles Transnational Corp. All rights reserved.  
The contents of this document are confidential and proprietary to Quintiles Transnational Corp. Unauthorized use, disclosure or reproduction is strictly prohibited.

Visit	Protocol Study Day	Deviation if outside	Visit Window relative to date of first study drug administration
Screening visit (Week -4: )	Day -28 to -1	+ 5 days	Week -4: Day -33 to Day -1
Study day 1 visit	1	Not applicable	
Dose titration period visits	Week 2: Day 14 Week 4: Day 28 Week 6: Day 42 Week 8: Day 56	± 3 days	Week 2: Day 11 to 17 Week 4: Day 25 to 31 Week 6: Day 39 to 45 Week 8: Day 53 to 59
Full dose Treatment visits	Week 10: Day 70 Week 12: Day 84 Week 14: Day 98 Week 16: Day 112 Week 18: Day 126	± 3 days	Week 10: Day 67 to 73 Week 12: Day 81 to 87 Week 14: Day 95 to 101 Week 16: Day 109 to 115 Week 18: Day 123 to 129
Follow-up visits (Week 22)	Week 22: Day 154	± 3 days,	Week 22: Day 151 to 157
Follow-up visits (Week 30)	Week 30: Day 210	± 7 days	Week 30: Day 203 to 217

Study day is calculated relative to the date of first administration of study drug and is only presented for subjects with a study drug administration date (see section 6.1 ).

The ET visit will be allocated to a scheduled visit according to the table above, where the ET visit has occurred in place of the scheduled visit and is within the relevant visit window. Any ET visits will be reviewed for allocation to a scheduled visit, at the DR meeting.

Document: ATX\_GD\_59 Final 1.0 SAP 28FEB2018.docx  
Author: [name]

Version Number: Final 1.0  
Version Date: 28FEB2018

Template No: CS\_TP\_BS016 Revision 4  
Effective Date: 01Apr2016

Reference: CS\_WI\_BS005

Copyright © 2009, 2010, 2012, 2016 Quintiles Transnational Corp. All rights reserved.  
The contents of this document are confidential and proprietary to Quintiles Transnational Corp. Unauthorized use, disclosure or reproduction is strictly prohibited.

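### TSH percentage and fold change divide by the assay quantification limit for nearly all subjects, so their magnitude cannot be interpreted, and no table counts subjects whose TSH becomes quantifiable

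*SAP*

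**What the plan says.** Inclusion criterion 3 in the protocol synopsis asks for raised free T3 and/or free T4, "including undetectable levels of thyroid stimulating hormone".

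SAP 6.2 sets the analysis baseline: "baseline is defined as the last available assessment (scheduled or unscheduled) prior to the first administration of study drug".

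For low results, SAP 14.1.3.3 states: "TSH level results that are below the limit of quantitation (BLQ) will be treated as value for descriptive statistics". I read this as entering the limit itself. The general laboratory rule in SAP 15.2 supports that reading, since a result reported as less than X "will be converted to X for the purpose of quantitative summaries". The size of the limit is left open: "The BLQ levels will be confirmed by Apitope or the IQVIA Central Laboratory prior to database lock".

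SAP 6.7.2 then gives the calculation: "For FT3, FT4 and TSH, percentage (%) change from baseline will be calculated as", followed by post-dose minus baseline, over baseline, times 100. It makes no exception for a baseline below the limit. Sections 4.3.4 and 14.1.3.3 have the result summarised for TSH at each post-baseline visit, and the 14.1.3.3 listing adds fold change for TSH. Under section 6.6 the percentage change is summarised by arithmetic mean, SD, minimum, quartiles, median and maximum; the geometric mean is left out for this quantity.

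For TSH, 14.1.3.3 also plans observed values, absolute change from baseline, and a shift table by reference-range category (low, normal, high, with markedly high as a subcategory).

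**The concern.** A percentage change needs a measured baseline to have a meaningful size. Here the entry criterion selects subjects whose TSH is too low to measure, and the plan substitutes the limit. The printed mean and SD then carry a scale factor that belongs to the assay.

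TSH is a named secondary endpoint. SAP 4.3.4 drops the responder endpoint partly because dichotomising loses the magnitude of response, and in the same place offers percentage change alongside absolute change. For TSH, magnitude is what percentage change cannot supply.

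A related gap is that the simplest sign of TSH recovery, a result moving from below the limit to above it, is not counted. In the shift table a subject who goes from undetectable to detectable but still under the reference range reads as low at both visits.

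**Working it through.** **Inputs.** The formula is from SAP 6.7.2 and the substitution rule from SAP 14.1.3.3. The plan gives no TSH figure to reproduce and no value for the limit L. I therefore assume L from 0.005 to 0.1 mIU/L, an illustrative recovery to 1.0 mIU/L, and 12 subjects with a common limit and baselines all below it.

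**Step 1: algebra.** With baseline entered as L:

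- percentage change = 100 × (post − L)/L = 100 × (post/L − 1);
- post-dose result also below L, so entered as L: 100 × (L/L − 1) = 0%;
- post-dose result at or above L: zero or positive. A negative value cannot arise;
- fold change (SAP 6.7.4) = exp(ln post − ln L) = post/L, with the same divisor.

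**Step 2: one subject rising to 1.0 mIU/L.**

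| Assumed L (mIU/L) | Percentage change | Fold change | Absolute change (mIU/L) |
|---|---|---|---|
| 0.005 | +19,900% | 200 | 0.995 |
| 0.01 | +9,900% | 100 | 0.99 |
| 0.1 | +900% | 10 | 0.90 |

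**Step 3: summary over 12 subjects.** If one subject reaches 1.0 and eleven stay below L, the mean is v/12 and the SD is v/√12, where v is the single non-zero value. If three reach 1.0, the mean is 3v/12.

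| Assumed L | Mean, 1 of 12 | SD, 1 of 12 | Mean, 3 of 12 | Mean absolute change, 3 of 12 (mIU/L) |
|---|---|---|---|---|
| 0.005 | 1,658% | 5,745 | 4,975% | 0.249 |
| 0.01 | 825% | 2,858 | 2,475% | 0.247 |
| 0.1 | 75% | 260 | 225% | 0.225 |

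With three recoveries the mean percentage change differs 22-fold across the assumed limits (4,975/225 = 22.1). The mean absolute change differs by a factor of about 1.1 (0.249/0.225). The median percentage change is 0% throughout.

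**Step 4: mixed baselines.** Take L = 0.01. A subject with a detectable baseline of 0.03 who reaches 1.0 gets 100 × (1.0 − 0.03)/0.03 = 3,233%. A subject from below the limit with the same post-dose result gets 9,900%. Any detectable baseline therefore puts a different divisor into the same mean.

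**Step 5: what is kept.** With one L and baselines below it, the percentage change is an exact linear function of the post-dose value as entered. Sign and the order of subjects are preserved; only the scale is arbitrary.

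**The case against.** The case for leaving the plan alone has real content.

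- **Other TSH summaries exist.** Section 6.6 prints median, quartiles and maximum, and 14.1.3.3 covers observed values and absolute change. With a common limit, a subject rising above it moves the observed maximum. SAP 15.2 lists out-of-range TSH by subject, and listings show low results with a less-than sign. A reader might infer that TSH recovery is visible nowhere; the documents do not support that. What is missing is a count.
- **The statistic is not empty.** A reader might also infer that it reflects only the assay limit and says nothing about change under treatment. That goes too far. SAP 14.1 sends TSH to one central laboratory, and under a common limit direction and order survive. The several-fold differences above compare hypothetical assays, not results within this study.
- **Eligibility does not strictly fix the analysed baseline.** Baseline is the last pre-dose value, the screening window is "Week -4: Day -33 to Day -1", and the ITT population disregards eligibility. The protocol's undetectable and the SAP's BLQ are also never formally linked. Hence nearly all subjects, not every subject. The exceptions do not help, because they mix divisors (step 4).
- **Little depends on it.** All presentations are descriptive. The paired tests and correlations in 14.2.2 leave TSH out, as do the change and percentage-change figures.

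These points limit the consequence. None gives the TSH percentage change an interpretable size.

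**Conclusion.** The point holds in limited form. Followed exactly, the SAP prints by-visit means and SDs of TSH percentage change, and lists TSH fold changes, whose size is set for nearly all subjects by a quantification limit that the documents do not state. Direction is kept, and so is order among subjects whose baseline is below the limit; magnitude is not interpretable. Separately, no planned table counts subjects whose TSH becomes quantifiable.

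The algebra rests on reading 14.1.3.3 as substituting the limit, and on undetectable TSH at entry appearing as a baseline below that limit. The sizes (+19,900% to +900% for one recovery) also rest on the assumed limits and the assumed post-dose value. The documents do not support concluding that the TSH endpoint as a whole is lost, or that FT3 and FT4 are affected. This is a defect in one descriptive secondary summary, worth correcting because it is cheap to do so.

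**What to change.** 1. Remove TSH from the percentage change in SAP 4.3.4, 6.7.2 and 14.1.3.3, and from the percentage-change and fold-change columns of the thyroid listing in 14.1.3.3.
2. Add, by visit, n (%) of subjects with TSH at or above the quantification limit, and state the confirmed limit with the table.
3. Keep the TSH observed-value, absolute-change and shift summaries. Leave FT3 and FT4 as they are.

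The cost is a few lines of SAP text, the matching table and listing shells, and one count row. No new data are needed. No planned figure, paired test or correlation uses TSH percentage or fold change, so nothing else has to be reworked.
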